3.1 Population

Three hundred participants will be included. Men and women aged 18 to 80 yrs, at risk for metabolic syndrome, will be eligible.

3.2 *Sample size calculation*

In each pilot intervention, 100 participants will be divided in 5 subgroups of 20 participants, each receiving a BEF within a specific food matrix (dairy-, bakery-, egg products) enriched with DHA, BG or AC alone, or DHA+BG, or DHA+AC. In this exploratory study, within each matrix, 20 subjects per arm would be sufficient to obtain measurable changes for the parameters that will be tested.

3.3 *Inclusion criteria*

MS is defined when three of the following criteria are met:

- elevated waist circumference (men \geq 102 cm; women \geq 88 cm)
- elevated fasting triglycerides (\geq 150 mg/dL)
- reduced fasting HDL-cholesterol (men \leq 40 mg/dL; women \leq 50 mg/dL)
- elevated blood pressure (systolic \geq 130 mmHg and/or diastolic \geq 85 mmHg) or hypotensive treatment
- elevated fasting glucose (\geq 110 mg/dL)

Subjects will be eligible to the pilot study if they present with two to four of the MS criteria, at least one of them being alteration of fasting triglycerides or HDL-C cholesterol.

3.4 *Exclusion criteria*

Participants are excluded if three or more clinical criteria for metabolic syndrome are met. Additionally, major exclusion criteria are:

- regular drug therapy with impact on serum lipids;
- diabetes (fasting glucose $>$ 1.26 g/L, or anti-diabetic treatment);
- recent history of cancer or cancer treatment (less than 2 years);
- active or recently diagnosed intestinal malabsorption or disorders associated with malabsorption: Crohn's disease, short bowel syndrome, Pancreatic insufficiency, cystic fibrosis, Tropical Sprue, whipple's disease, chronic pancreatitis, gastrojejunostomy, surgical treatments for obesity, cholestasis, biliary atresia, parasite infections, HIV/AIDS
- familial dyslipidemia;
- use of medication known to cause malabsorption: tetracycline, cholestyramine, thiazide diuretics, aluminium/magnesium hydroxide, cochlincine, neomycin, methotrexate, methyl dopa, and allopurinol, and laxatives
- illegal drug use, chronic alcoholism or active smoking;
- consumption of nutritional supplements containing DHA, BG or AC;
- history of allergy or intolerance to any components used in BEFs, celiac disease, lactose intolerance, allergy to milk or egg proteins;
- institutionalised patients, those who lack autonomy to consent or are unable to meet all examinations;

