Range of analysis:

For serum samples, the method is linear for the following range:

5–115 mg/dL or 0.1–3.0 mmol/L

Conversion factor: mg/dL x 0.0259 = mmol/L

Precision

Each instrument will have specific performance ranges, but generally the percentage coefficient of variation (%CV) should be below 3%. Replicate analyses will be performed for each sample.

Expected values

Low (undesirable, high risk): < 40 mg/dL (< 1.0 mmol/L) for men < 50 mg/dL (< 1.0 mmol/L) for women

There is no clinical significant value at which medical team should be contacted.

HDL-cholesterol values are not affected by fasting.

Recording of results

Results will be collected by the clinical researcher and entered into the database for statistical analyses. Any abnormal results will be reported to the principal investigator.

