9.10 Food consumption record

Food consumption record

Screening ID

Randomisation ID

You are required to eat 2 pancakes from each packet every day.

Please use this sheet to record each day that you eat the pancakes, and note any days that you do not eat them. Also write down if you only eat part of the portion.

The researcher will highlight your start and end dates on this sheet.

Today's date _____

Researcher signature _____

	Mon	Tue	Wed	Thu	Fri	Sat	Sun
Week 1							

	Mon	Tue	Wed	Thu	Fri	Sat	Sun
Week 2							

	Mon	Tue	Wed	Thu	Fri	Sat	Sun
Week 3							

	Mon	Tue	Wed	Thu	Fri	Sat	Sun
Week 4							

	Mon	Tue	Wed	Thu	Fri	Sat	Sun
Week 5							

Thank you for your help!

9.11 Clinical Research File – Screening – Visit 1

Visit 1 Screening CRF

Contact details	
ID	
First name	
Surname	
Telephone number	
Mobile number	
Email	
Home address	

General information		
Gender	MALE	FEMALE
Date of Birth		<18 or >80 y = exclude (<January 1934 to September 1996>)

Date & Time of examination:

Physical examination	Measurement	Fits MS Criterion? (Y / N)	MS Criterion
Height (m)			
Weight (kg)			
Waist circumference (cm)			Male ≥102 cm Female ≥88 cm
Systolic BP (mm Hg)			≥130 mm Hg
Diastolic BP (mm Hg)			≥85 mm Hg

Date & Time of blood collection:

Blood analysis	Analyte concentration	Fits MS Criterion? (Y / N)	MS Criterion
Triglycerides (mg/dL)			≥150 mg/dL
Total cholesterol (mg/dL)			
HDL-cholesterol (mg/dL)			Male ≤40 mg/dL Female ≤50 mg/dL
Glucose (mg/dL)			≥110 mg/dL

MS criteria met (please tick those which apply)

Waist Circumference	Blood Pressure (SBP &/or DBP)	Triglycerides	HDL-cholesterol	Glucose	Number of MS criteria met

Continue to page 2

GP contact details	
GP name	
Surgery name	
Telephone number	
Surgery address	

End of Visit 1 Screening CRF

Visit 2 Baseline CRF

Randomisation ID

Screening ID

Date & Time of examination:

.....

Physical examination	Measurement	Fits MS Criterion? (Y / N)	MS Criterion
Height (m)			
Weight (kg)			
Waist circumference (cm)			Male ≥102 cm Female ≥88 cm
Systolic BP (mm Hg)			≥130 mm Hg
Diastolic BP (mm Hg)			≥85 mm Hg

Date & Time of blood collection:

.....

Blood analysis	Analyte concentration	Fits MS Criterion? (Y / N)	MS Criterion
Triglycerides (mg/dL)			≥150 mg/dL
Total cholesterol (mg/dL)			
HDL-cholesterol (mg/dL)			Male ≤40 mg/dL Female ≤50 mg/dL
Glucose (mg/dL)			≥110 mg/dL

MS criteria met (please tick those which apply)

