Waist Circumference	Blood Pressure (SBP &/or DBP)	Triglycerides	HDL-cholesterol	Glucose	Number of MS criteria met

Continue to page 2

Questions about your lifestyle			
Females only: Are you pregnant, lactating or actively trying to conceive?	YES	NO	Yes = exclude
Females only: Are you currently using any contraceptive treatment or hormone replacement therapy?	YES	NO	
Do you smoke?	YES	NO	Yes = exclude
Do you use recreational drugs?	YES	NO	Yes = exclude
Do you drink alcohol?	YES	NO	
If yes , how much?	(day / week)		Male ≥ 5 units/d = exclude Female ≥ 4 units/d = exclude
As a guide, 1 pint of beer / 1½ bottles of lager / 1 medium (175 mL) glass of wine = 2-3 units			
Do you take any dietary supplements?	YES	NO	
If yes , give details.			DHA, AC, Fibre = exclude
Are you on any kind of diet?	YES	NO	
Do you regularly play sport or exercise?	YES	NO	
If yes , how often and for how long?			

Questions about your health			
Have you ever been told that you have any of the following?			
High blood pressure	YES	NO	
High blood triglycerides	YES	NO	
Altered blood cholesterol	YES	NO	
High blood glucose	YES	NO	

Continue to page 3

Questions about your health continued			
Do you have a family history of high blood lipids?	YES	NO	Yes = exclude
Do you have an allergy or intolerance to any food?	YES	NO	
If yes , give details.			Lactose, milk, egg, any other ingredient of BEF = exclude
Have you ever been diagnosed with any of the following?			
Celiac disease	YES	NO	Yes = exclude
Intestinal disorders (Crohn's disease, short bowel syndrome, pancreatic insufficiency, cystic fibrosis, tropical sprue, whipple's disease, chronic pancreatitis, gastrojejunostomy, surgical treatment for obesity, cholestasis, biliary atresia, parasite infections)	YES	NO	Yes = exclude
Diabetes	YES	NO	Yes = exclude
Heart disease	YES	NO	Yes = exclude
Liver disease	YES	NO	Yes = exclude
Kidney disease	YES	NO	Yes = exclude
Cancer	YES	NO	
If yes , when did treatment end?			End of treatment <2 y = exclude
Any other disease in the last 2 years	YES	NO	Yes = check if relevant
If yes , give details.			
Are you currently taking or do you regularly take any prescription or non-prescription medicine?	YES	NO	
If yes , give details.			Statins, fibrates, tetracycline, cholestyramine, thiazide diuretics, aluminium/magnesium hydroxide, cochlincine, neomycin, methotrexate, methyldopa, allopurinol, warfarin, other anticoagulant/lipid lowering, laxatives = exclude

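### The screening forms do not apply the blood-pressure criterion of 3.3 or the lipid-disorder exclusion of 3.4 as written; a minor slip in the HDL SOP misconverts the women's cut-off

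*Protocol*

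**What the plan says.** **Blood pressure.** Protocol 3.3 lists five metabolic-syndrome criteria and bases entry on how many are met. The blood-pressure criterion is met by a systolic value of at least 130 mmHg and/or a diastolic value of at least 85 mmHg, "or hypotensive treatment". On the Visit 1 and Visit 2 CRFs (9.11, 9.12) the criterion column shows only the two measured thresholds. The box that feeds the number of criteria met is labelled "Blood Pressure (SBP &/or DBP") and has no place for treatment.

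**Lipid disorder.** Protocol 3.4 excludes "familial dyslipidemia". The Visit 2 CRF and the telephone questionnaire (9.14) instead ask "Do you have a family history of high blood lipids", and a positive answer is marked as an exclusion.

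**HDL-C units.** SOP 9.5 gives the "Conversion factor: mg/dL x 0.0259 = mmol/L". Under its expected values it prints "< 40 mg/dL (< 1.0 mmol/L) for men" and "< 50 mg/dL (< 1.0 mmol/L) for women".

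**The concern.** The forms are what staff complete when deciding on entry. Where a form differs from 3.3 or 3.4, following the form gives a different decision from following the protocol. The blood-pressure difference changes the criteria count, which has both a lower and an upper limit. The lipid-history difference acts separately, as an exclusion: it is wider than 3.4 in one direction and narrower in the other. The HDL-C line attaches the same mmol/L value to two different mg/dL cut-offs, so one of them must be wrong. At stake is which people make up the enrolled population, and whether it is the one that 3.3–3.4 describe.

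**Working it through.** **1. Blood pressure: the count under 3.3 and on the form.** Take a participant on an antihypertensive drug with readings below 130/85. Section 3.3 scores blood pressure as met; the form scores it as not met. The form's count is therefore always one lower.

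| Other criteria met (at least one of them TG or HDL-C) | Count under 3.3 | Count on the form | Limit affected |
|---|---|---|---|
| 1 | 1 + 1 = 2 | 1 | Lower limit of two (3.3): protocol admits, form refuses |
| 2 | 2 + 1 = 3 | 2 | Upper limit if 3.4 (three or more excluded) governs: protocol excludes, form admits |
| 4 | 4 + 1 = 5 | 4 | Upper limit if 3.3 (two to four) governs: protocol excludes, form admits |

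Sections 3.3 and 3.4 disagree on the upper limit, so two rows are needed for it. The undercount crosses a limit under either reading.

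Could the forms recover the information? The telephone form and Visit 2 CRF ask about past high blood pressure and about current medicines. No instruction carries either answer into the count, and the Visit 1 CRF as shown has no medicines item. Section 3.4 already excludes users of thiazide diuretics and methyldopa, so the people affected are those on other antihypertensives.

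**2. Lipid disorder: 3.4 beside the forms.** Section 3.4 concerns a condition of the participant. The form item concerns relatives. Two mismatches follow:

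- A person with an affected relative but no familial dyslipidaemia is not excluded by 3.4 on this ground, but is refused by the form.
- A person with familial dyslipidaemia who reports no family history is excluded by 3.4 but passes this item. The items on having been told of high triglycerides or altered cholesterol carry no exclusion. The medicines item would catch such a person only if they take a listed drug such as a lipid-lowering agent.

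This item does not enter the criteria count.

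**3. HDL-C conversion.** Inputs, all from SOP 9.5: the factor 0.0259, the linear range "5–115 mg/dL or 0.1–3.0 mmol/L", and the two cut-offs. Formula: mmol/L = mg/dL × 0.0259.

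| mg/dL | × 0.0259 | Printed mmol/L | Agrees? |
|---|---|---|---|
| 5 | 0.1295 | 0.1 | yes |
| 115 | 2.9785 | 3.0 | yes |
| 40 (men) | 1.036 | 1.0 | yes |
| 50 (women) | 1.295 | 1.0 | no |

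Converted back, 1.0 / 0.0259 = 38.6 mg/dL. The two printed forms of the women's cut-off therefore differ by 50 − 38.6 = 11.4 mg/dL. The factor reproduces the other HDL-C figures, so the isolated error is the women's mmol/L value. The SOP also uses a strict < where 3.3 and the CRFs use ≤.

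**The case against.** The strongest reply is that 3.3 and 3.4 govern. SOP 9.1 requires the inclusion and exclusion criteria to be verified before enrolment, and medicines and blood-pressure history are collected, so a careful researcher could still reach the right count. That limits the harm but does not remove the contradiction: the tally as printed leaves treatment out, and the lipid-history item tells staff to exclude.

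Four stronger readings might be inferred. The documents do not support them.

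- *Women with HDL-C between 38.6 and 50 mg/dL are misclassified at entry.* Section 3.3 sets the criterion in mg/dL, and the CRFs record HDL-C in mg/dL with the correct women's cut-off of 50 beside the entry. The wrong figure is in a laboratory SOP's expected values and could act only if results are flagged in mmol/L.
- *Every mismatch shifts the criteria count.* Through the forms, only the blood-pressure omission does.
- *Enrolment differs by centre, so the errors confound the food matrix.* Section 3.5 has the centres share the eligibility questionnaire, 5.6 applies the annexed SOPs at all three, and section 7 harmonises the screening questionnaires. Nothing shows that eligibility items differ between centres. Randomisation is within centre, so a form error acts on all five arms alike.
- *The additional form exclusions (heart, liver and kidney disease, anticoagulants) contradict 3.4.* Section 3.4 introduces its list as the major criteria, so it does not claim to be complete.

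**Conclusion.** The point holds for two mismatches that decide entry. First, the CRF tally is one criterion short for any participant on antihypertensive treatment with normal readings, enough to cross the lower limit or whichever upper limit applies. Second, the lipid-disorder exclusion on the forms is not the one in 3.4 and can err in both directions. Both conclusions assume that staff follow the forms as printed. The documents give no figure for the share of volunteers who are treated or who have a family history of raised lipids, so the number affected cannot be stated. The effect is on who is enrolled, not on the validity of the randomised comparison between arms within a centre.

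The HDL-C figure is a minor error of arithmetic (1.0 printed, about 1.3 mmol/L by the SOP's own factor), with no documented route to an eligibility decision.

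**What to change.** Before screening starts:

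1. Reconcile the Visit 1 and Visit 2 CRFs with 3.3, so that the criterion rows, the tally box and the protocol use one blood-pressure criterion. If treatment counts, the form needs a prompt that carries the medicines answer into the tally. The Visit 3 CRF has no role in eligibility.
2. Reconcile the lipid-history item on the telephone form and Visit 2 CRF with 3.4, so that both state one exclusion. The sponsor decides which wording stands for items 1 and 2.
3. In SOP 9.5, correct the women's value to about 1.3 mmol/L (1.295 by its factor) and align < with the ≤ of 3.3 and the CRFs.
4. As a harmonisation note only: say in 3.4 whether the additional exclusions on the forms apply. The telephone form also excludes exercise of 5 hours or more per week, which the Visit 2 CRF does not.

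The cost is edits to one SOP and three forms, or to 3.3–3.4 if the sponsor keeps the form wording. No additional participants are needed.

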9.6 SOP Quantification of triglycerides in serum samples

Standard Operating Procedure (SOP) Quantification of triglycerides in serum samples

Purpose and scope

This SOP describes the procedures that all study personnel will use when analyzing serum samples for the quantitative determination of serum triglycerides as part of PATHWAY-27 WP5, while ensuring the safety and welfare of subjects and staff involved in the study.

Responsible persons

Principal investigator

The principal investigator is responsible and accountable for:

1. Ensuring that the equipment is fit for purpose.
2. Ensuring that all staff is suitably trained in all aspects of the procedure, including the safe handling of blood-derived samples and chemicals.
3. Notifying the WP leader of any deviations, safety breaches or abnormal results.
4. Keeping record of the code of all subjects entering the study, guaranteeing their data will be anonymous

Clinical researcher or manager

The clinical researcher or manager is responsible for:

1. Reporting to the principal investigator the results of analysis and logs of all procedures undertaken, highlighting any deviations, safety breaches or abnormal results
2. Operator
3. The operator is responsible for:
4. Following all procedures according to the SOP and instructions provided, including the keeping of logs of calibration and control procedures.
5. Notifying the clinical researcher/manager or principal investigator of any deviations or abnormal results.

Procedures

Name of the method

Automated enzymatic colorimetric method for determination of triglycerides.

Purpose

For the in vitro diagnostic use in the quantitative determination of triglycerides from serum using an automated blood analyser.

Principle

The method relies on the enzymatic hydrolysis of triglycerides to fatty acids and glycerol. Glycerol is then oxidized to dihydroxyacetone and hydrogen peroxide. Hydrogen peroxide can be measured following a Trinder endpoint reaction, the products of which can be detected by colorimetry at wavelengths >505 nm. The single reagent procedure measures total triglycerides including the mono and diglycerides and the free glycerol fractions.

Equipment

Automated blood analyser. Manufacturer varies between countries therefore cannot be harmonized. However, the analyses will focus on variations of this parameter from d0 to d28 that would not be affected by the lack of analyser harmonisation.

Reagents

Reagents will be purchased, prepared and stored according to the equipment manufacturer's instructions.

Calibration of the equipment

The equipment will be calibrated according to manufacturer's instructions. Calibrations will be performed:

- Every time that the equipment is switched off
- Every time that the equipment is cleaned or maintained
- Every time that any trouble shooting procedures have been undertaken
- Every time that any of the reagents or optical components are changed
- Each instrument brand/model has a maximum calibration stability that must be complied to. Calibration standards will be applied according to manufacturer Instructions. A log of calibrations will be kept including the date, the lot number of the reagents used, the date the reagents were first opened and their expiry date.

Quality control

Appropriate control tests will be routinely performed using control samples (upper and lower limit controls). Each laboratory may have its own quality control procedures, but as a minimum, these control tests will be performed:

- Twice daily
- After each calibration
- If there are any issues with analyses that suspect deviations from the normal range of analysis
- Quality control standards will be purchased and used according to the manufacturer's instructions. A log of quality control tests will be kept including the date, the lot number of reagents used, the date the reagents were first opened, and their expiry date.

Samples

Serum will be used for analysis.

- Sera will be collected, prepared and stored according to SOP.
- Before analysis, the operator will check that check the tubes for signs of leakage or contamination, and will check that the labelling is correct for the type of test requested. The operator shall keep a record of the samples analysed by subject's code.
- Minimum volumes drawn will be in accordance with manufacturer instructions.
- Unconjugated bilirubin and haemoglobin interfere significantly (>10% interference) with the assay. Haemolysis should be avoided during blood collection and serum preparation.
- Details of how the serum should be handled and loaded onto the machine will adhere to manufacturer's instructions.

Range of analysis:

For serum samples, the method is linear for the following range:

0 to 550 mg/dL (0 to 6.22 mmol/L)

Conversion factor: mg/dL x 0.0113 = mmol/L

Precision

Each instrument will have specific performance ranges, but generally the percentage coefficient of variation (%CV) should be below 4%. Replicate analyses will be performed for each sample.

Expected values

Normal fasting < 150 mg/dL (<1.70 mmol/L)

Normal non-fasting: < 250 mg/dL (< 2.83 mmol/L)

Borderline high: 250–500 mg/dL (2.83–5.65 mmol/L)

Hypertriglyceridemia: > 500 mg/dL (> 5.65 mmol/L)

High risk for pancreatitis: > 1000 mg/dL (> 11.30 mmol/L)

Triglyceride levels > 1000 mg/dL will be notified to the participant medical doctor.

Recording of results

Results will be collected by the clinical researcher and entered into the database for statistical analyses. Any abnormal results should be reported to the principal investigator.

9.7 SOP Quantification of glucose in blood samples

Standard Operating Procedure (SOP) Quantification of glucose in blood samples

Purpose and scope

This SOP describes the procedures that all study personnel will use when analyzing blood samples for the quantitative determination of glucose as part of PATHWAY-27 WP5, while ensuring the safety and welfare of subjects and staff involved in the study.

Responsible persons

Principal investigator

The principal investigator is responsible and accountable for:

- Ensuring that the equipment is fit for purpose.
- Ensuring that all staff is suitably trained in all aspects of the procedure, including the safe handling of blood-derived samples and chemicals.
- Notifying the WP leader of any deviations, safety breaches or abnormal results.
- Keeping record of the code of all subjects entering the study, guaranteeing their data will be anonymous.

Clinical researcher

The clinical researcher or manager is responsible

- Reporting to the principal investigator the results of analysis and logs of all procedures undertaken, highlighting any deviations, safety breaches or abnormal results

Operator

The operator is responsible for:

- Following all procedures according to the SOP and instructions provided, including the keeping of logs of calibration and control procedures.
- Notifying the clinical researcher/manager or principal investigator of any deviations or abnormal results.

Procedures

Name of the method

Automated enzymatic colorimetric method for determination of glucose.

Purpose

For the in vitro diagnostic use in the quantitative determination of glucose from blood using an automated blood analyser.

Principle

The method relies on the enzymatic oxidation of glucose to gluconic acid and hydrogen peroxide. Hydrogen peroxide can be measured following a Trinder endpoint reaction, the products of which can be detected by colorimetry at wavelengths >505 nm. It is a single-reagent, endpoint procedure.

Equipment

Automated blood analyser. Manufacturer varies between countries therefore cannot be harmonized. However, the analyses will focus on variations of this parameter from d0 to d28 and would not be affected by the lack of analyser harmonisation.

Reagents

Reagents will be purchased, prepared and stored according to the equipment manufacturer's instructions.

Calibration of the equipment

The equipment should be calibrated according to manufacturer's instructions. Generally calibrations should be performed:

- Every time that the equipment is switched off
- Every time that the equipment is cleaned or maintained
- Every time that any trouble shooting procedures have been undertaken
- Every time that any of the reagents or optical components are changed
- Each instrument brand/model will have a maximum calibration stability that should be complied to. Calibration standards will be applied according to manufacturer Instructions. A log of calibrations should be kept including the date, the lot number of the reagents used, the date the reagents were first opened and their expiry date.

Quality control

Appropriate control tests should be routinely performed using control samples (upper and lower limit controls). Each laboratory may have its own quality control procedures, but as a minimum, these control tests should be performed:

- Twice daily
- After each calibration
- If there are any issues with analyses that suspect deviations from the normal range of analysis
- Quality control standards should be purchased and used according to the manufacturer's instructions. A log of quality control tests should be kept including the date, the lot number of reagents used, the date the reagents were first opened, and their expiry date.

Samples

Blood will be used for analysis.

- Blood should be collected, prepared and stored according to SOP.
- Before analysis, the operator should check that check the tubes for signs of leakage or contamination, and should check that the labelling is correct for the type of test requested. The operator shall keep a record of the samples analysed by subject's code.
- Minimum volumes drawn will be in accordance with manufacturer instructions.
- Unconjugated and conjugated bilirubin, lipids and ascorbic acid are some of the interfering substances (>10% interference).
- For details of how the serum should be handled and loaded onto the machine, please adhere to manufacturer's instructions.

Range of analysis:

For blood samples, the method is linear for the following range:

to 750 mg/dL (0.3 to 41.6 mmol/L)

Conversion factor: mg/dL x 0.0555 = mmol/L

Precision:

Each instrument will have specific performance ranges, but generally the percentage coefficient of variation (%CV) should be below 3%. Replicate analyses should be performed for each sample.

Expected values:

Normal range: 74–106 mg/dL (4.1–5.9 mmol/L)

High fasting: ≥ 110 mg/dL (> 6.1 mmol/L)

For the first glucose measurement (the one for setting if the volunteer is eligible), glucose levels showing diabetes or hypoglycemia will be notified to the participant and to his medical doctor and the participant will not be included in the trial. If unexpected high glucose level is found at the end of the trial the volunteer will be alert after his/her code is broken. In such case, the volunteer will not be excluded.

Recording of results:

Results will be collected by the clinical researcher and entered into the database for statistical analyses. Any abnormal results should be reported to the principal investigator.

